	
measure, women of childbearing potential will not be included in the study temporarily.
 
• If the visit cannot be performed in person, the study subject should take a photograph of the vaccination site or show it over live video call to the Investigator who will document the assessment. Photo or live video call will be deleted after assessment. Vaccination site inspection:
• If subject does not have a cutaneous reaction (presence of induration, erythema and/or a characteristic papule lesion) at the vaccination site by Day 7, there is no confirmation of vaccination 'take'. As these subjects do not develop an immune response to the vaccination and are unlikely to be at risk of vaccination complications, further follow-up will be conducted by phone on Day 12, and Day 28. These non-responder subjects are not eligible for plasmapheresis. If non-responders are not able to attend End of Study (Day 35 \pm3) visit in person at the site, the visit can be conducted over video conference or a phone call. For non-responders, no Final Safety Assessment at Day 90 (\pm3) will be necessary. All female subjects of childbearing potential must undergo a urine pregnancy test at Day 35 post-vaccination, regardless of 'take' status. As a COVID-19 precautionary measure, women of childbearing potential will not be included in the study temporarily.• Unanticipated problems.• All adverse events including all cardiovascular adverse events (symptoms and signs).• Diary card review and verification against adverse events collection above.• Concomitant medications.• Review vaccination site care instructions and provide vaccination site dressing kit. 
Post-vaccination Day 12 (\pm2), 21 (\pm3), and 28 (\pm3)

--	---

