^g Postmenopausal is defined as either >12 consecutive months with no menses without an alternative medical cause or FSH ≥ 40 mIU/mL; if these criteria are not met and the woman is >50 years, she may participate if she agrees to undergo pregnancy testing requirements and agrees to use an effective birth control

Assessment	Screening (Within 14 Days Before Baseline) ^c	Baseline (Day 0)	Day 3 (±1)	Day 7 (±1) ^h	Day 12 (±2)	Day 21 (±3)	Day 28 (±3)	End of Study Day 35 (±3) or Early Withdrawal	Follow-up Weekly Visits for Unresolved Adverse Reactions	Final Safety Assessment Day 90 (±3)
------------	--	---------------------	------------------	----------------------------------	-------------------	-------------------	-------------------	---	--	---

method such as barrier contraception for 4 weeks post-vaccination or until scab separates, whichever is longer. As a COVID-19 precautionary measure, women of childbearing potential will not be included in the study temporarily.

^hIf subject does not have a cutaneous reaction (presence of induration, erythema and/or a characteristic papule lesion) at the vaccination site by Day 7, there is no confirmation of vaccination 'take'. As these subjects do not develop an immune response to the vaccination and are unlikely to be at risk of vaccination complications, further follow-up will be conducted by phone on Day 12 and Day 28. These non-responder subjects are not eligible for plasmapheresis. All non-responders will attend End of Study (Day 35 ±3) visit in person at the site. For non-responders no Final Safety Assessment at Day 90 (±3) will be necessary. All female subjects of childbearing potential must undergo a urine pregnancy test at Day 35 post-vaccination, regardless of 'take' status. As a COVID-19 precautionary measure, women of childbearing potential will not be included in the study temporarily.

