6.4 Post-vaccination Day 7 (± 1)

- Identify if any exclusion criteria have arisen (i.e. skin conditions, living conditions/close contacts, pregnancy).
- Assessment of pericarditis/myocarditis symptoms (see section [6.9](#)).
- Urine pregnancy test [females of childbearing potential (must be negative)]. In the event of a positive pregnancy test result, the pregnancy must be reported to Emergent and the *National Smallpox Vaccine in Pregnancy Registry*. As a COVID-19 precautionary measure, women of childbearing potential will not be included in the study temporarily.
- Vaccination site inspection (see section [6.3](#)). If the visit cannot be performed in person, the study subject should take a photograph of the vaccination site or show it over live video call to the Investigator who will document the assessment. Photo or video will be deleted after assessment.
 - If subject does not have a cutaneous reaction (presence of induration, erythema and/or a characteristic papule lesion) at the vaccination site by Day 7, there is no confirmation of vaccination 'take'. As these subjects do not develop an immune response to the vaccination and are unlikely to be at risk of vaccination complications, further follow-up will be conducted by phone on Day 12 and Day 28. These non-responder subjects are not eligible for plasmapheresis. All non-responders will attend End of Study (Day 35 ± 3) visit in person at the site. For non-responders no Final Safety Assessment at Day 90 (± 3) will be necessary. All female subjects of childbearing potential must undergo a urine pregnancy test at Day 35 post-vaccination, regardless of 'take' status. As a COVID-19 precautionary measure, women of childbearing potential will not be included in the study temporarily.
- Unanticipated problems.
- All adverse events including all cardiovascular adverse events (symptoms and signs).
- Diary card review and verification against AE collection above.
- Concomitant medications (see section [6.10](#)).
- Review vaccination site care instructions and provide vaccination site dressing kit (see section [6.2.3](#)).

6.5 Post-vaccination Weekly Follow-ups Days 12 (± 2), 21 (± 3), 28 (± 3) and Plasmapheresis

Plasmapheresis must not begin until at least 10 days after ACAM2000 vaccination. Donors will undergo plasmapheresis according to FDA approved site procedures.

Although plasmapheresis may occur up to biweekly during this period, the following study assessments will only be required once per week:

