6.6 End of Study Visit Day 35 (± 3) or Early Withdrawal

- Identify if any exclusion criteria have arisen (i.e. skin conditions, living conditions/close contacts, pregnancy).
- Vital signs (see section [6.1.2](#)). Assessment of pericarditis/myocarditis symptoms (see section [6.9](#)).
- Urine pregnancy test for female subjects of child bearing potential. In the event of a positive pregnancy test result, the pregnancy must be reported to Emergent and the *National Smallpox Vaccine in Pregnancy Registry*. As a COVID-19 precautionary measure, women of childbearing potential will not be included in the study temporarily. Vaccination site inspection. If the visit cannot be performed in person, the study subject should take a photograph of the vaccination site or show it over live video call to the Investigator who will document the assessment. Photo or live video call will be deleted after assessment.
- Unanticipated problems.
- All adverse events including all cardiovascular adverse events (symptoms and signs).
- Diary card review and verification against AE collection above.
- Concomitant medications (see section [6.10](#)).
- Review vaccination site care instructions and provide vaccination site dressing kit (required only if the scab has not separated) (see section [6.2.3](#)). If the visit cannot be performed in person, the study subject should take a photograph of the vaccination site or show it over live video call to the Investigator who will document the assessment. Photo or live video call will be deleted after assessment.

After the End of Study visit, eligible subjects may have the option to continue donating plasma as per the site's FDA approved SOPs for VIGIV plasma collection.

Note: If a subject's vaccination site has not completely healed by the Early Withdrawal Visit then efforts will be made to follow up with the subject until the vaccination site is completely healed. In addition, efforts will be made to conduct the Day 90 safety follow-up with the subject.

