6.7 Extended Follow-up Weekly Visits for Unresolved Adverse Reactions

All related AEs (serious and non-serious) will be followed to resolution or stabilization as applicable. Any vaccination scab that has not separated by 28 days after vaccination should be considered an AE.

If extended follow-up weekly visits are required, they will include:

- Identify if any exclusion criteria have arisen (i.e. skin conditions, living conditions/close contacts, pregnancy) (required only if the scab has not separated).
- Assessment of pericarditis/myocarditis symptoms (see section [6.9](#)).
- Urine pregnancy test [females of childbearing potential (must be negative)]. In the event of a positive pregnancy test result, the pregnancy must be reported to Emergent and the *National Smallpox Vaccine in Pregnancy Registry*. As a COVID-19 precautionary measure, women of childbearing potential will not be included in the study temporarily. Vaccination site inspection. If the visit cannot be performed in person, the study subject should take a photograph of the vaccination site or show it over live video call to the Investigator who will document the assessment. Photo or live video call will be deleted after assessment.
- Unanticipated problems.
- All adverse events including all cardiovascular adverse events (symptoms and signs).
- Diary card review and verification against AE collection above.
- Concomitant medications (see section [6.10](#)).
- Review vaccination site care instructions and provide vaccination site dressing kit (required only if the scab has not separated) (see section [6.2.3](#)).

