7.9 Adverse Event/Reaction Reporting

The following are adverse events of special interest that need to be reported to the sponsor's Pharmacovigilance department by phone (see section 7.10) within 24 hours of knowledge of the event: autoinoculation, cardiomyopathy, central nervous system disease, contact transmission of vaccinia, death, eczema vaccinatum, fetal vaccinia, generalized vaccinia, ischemic heart disease, ocular vaccinia, potential myocarditis and pericarditis, progressive vaccinia, Stevens-Johnson Syndrome, and superinfection of vaccination site.

Occurrence of adverse events will be reported into the eCRF and monitored throughout all phases of the study at all visits and will cover all participating subjects. Study subjects will be provided with a 24-hour telephone number to contact study personnel in case of an untoward reaction.

The Principal Investigator(s) will follow all adverse events for at least four weeks after the administration of ACAM2000 and throughout all phases of the study up to the final study visit. The related adverse events will be followed until resolution or stabilization as applicable.

According to CDC Reporting Guidelines (8) "Any adverse reaction that requires treatment with VIGIV should be reported immediately, and adverse events that meet the regulatory criteria for "serious" (i.e., those resulting in hospitalization, permanent disability, life-threatening illness, or death) should be reported within 48 hours; all other events should be reported within 1 week by the Principal Investigator." Vaccinia complications, including those in section 7.8.2, are also reportable to CDC.

If smallpox vaccination/vaccinia-related AEs are required to be reported to the site's State or Local Health Authority(ies), the Principal Investigator will be responsible for such reporting. If a complication arises, such as a second scab or satellite lesions close to the vaccination site, these AEs may not be considered reportable. The complications that arise within the area under the bandage can be handled according to instructions in this protocol for vaccination site care. Such expected vaccination reactions may only be considered reportable at the investigator's discretion considering subject and close contact safety, specifically the risk of vaccinia spread to self or others. Please review your site's relevant State and Local Health Authority reporting requirements as most states require reporting immediately or within 24 hours.

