ACAM2000[®] must be administered only by a qualified medical practitioner who has received training by Cangene Corporation to safely and effectively administer the vaccine by the percutaneous route (scarification) at baseline (Day 0), as required by FDA. All subjects will be followed to Day 35 post-vaccination, with a final safety assessment conducted on Day 90. Extended follow-up visits will be conducted for any unresolved serious adverse events and non-serious related adverse events, weekly or until resolution. Subjects with vaccination sites that have not healed will also be assessed at extended follow-up weekly visits until the vaccination site has completely healed.

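### Does the missing Day 90 assessment in subjects without a vaccine take undermine the pooled adverse event tables?

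*SAP*

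**What the plan says.** SAP section 1 describes follow-up as: "All subjects will be followed to Day 35 post-vaccination, with a final safety assessment conducted on Day 90". It names no exception.

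The protocol does. The synopsis (Day 7 visit) says "For non-responders, no Final Safety Assessment at Day 90" is needed. Schedule of Events footnote h and section 6.4 repeat this with "For non-responders no Final Safety Assessment at Day 90". All three apply to subjects with no cutaneous reaction at the site by Day 7. For these subjects section 6.4 says "further follow-up will be conducted by phone on Day 12 and Day 28", followed by an End of Study contact at Day 35. It adds: "These non-responder subjects are not eligible for plasmapheresis". The stated reason is that they mount no immune response and are unlikely to have vaccine complications.

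Two protocol provisions do not depend on take. Section 6.7 says "All related AEs (serious and non-serious) will be followed to resolution or stabilization as applicable". Section 7.9 has adverse events followed for at least four weeks and "throughout all phases of the study up to the final study visit", and gives every subject a 24-hour telephone number.

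On the analysis side, SAP section 4 defines one safety population of all vaccinated subjects. SAP section 6 counts each subject once per system organ class and preferred term. Tables 14.3.1.1 to 14.3.1.9 are arranged by term, relatedness, intensity, frequency and seriousness. None is arranged by take or by period. Onset day is given for each event in the listings.

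**The concern.** The Day 90 assessment collects all adverse events, unanticipated problems and pericarditis/myocarditis symptoms (protocol section 6.8). A reader who relies on SAP section 1 would take every adverse event percentage as resting on scheduled assessment to Day 90 in every subject. Under the protocol, scheduled assessment of non-takes stops at Day 35. The numerator for Days 36-90 would then come almost wholly from takes, while the denominator includes everyone. If non-takes were common, late events would look rarer than they are among the donors who were actually assessed.

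Safety is the only objective the SAP addresses, and only subjects with a take go on to give plasma, so incidence in that group is of natural interest. There is also a practical risk: a blank Day 90 entry in the pericarditis/myocarditis listing could be read as a missed contact when none was planned.

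**Working it through.** The plan states no figure on this point, so there is none to reproduce. The check has four steps.

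**1. Scheduled contacts after Day 7 (protocol sections 6.4 to 6.8).**
- Take: Days 12, 21, 28, 35 and 90, which is 5 contacts.
- No take: Days 12 and 28 by phone, and Day 35, which is 3 contacts.

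The schedules therefore differ, as the concern says. Section 7.9 does not by itself set different end points by take. Sections 6.6 and 9.2 treat Day 35 as the end of the study for everyone, apart from unresolved events, and Day 90 is a separate safety contact that may be made by phone.

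**2. What uses the SAP sentence.** SAP section 4 defines the denominator by vaccination, not by follow-up. SAP section 6 counts subjects with an event and sets no window. No Appendix I table refers to a Day 90 population. If the sentence were corrected or deleted, every planned table would come out the same.

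**3. How many subjects could be affected.** Let *f* be the fraction without a take. The documents give no value. Protocol section 7.8.1 calls non-takes rare and says essentially everyone vaccinated 25 or more years earlier should take. It also says shorter intervals make a non-take more likely, and entry is allowed from 3 years. Assume *f* = 1% to 5%.

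| *f* | non-takes of 750 | non-takes of 3000 | mean scheduled follow-up = 90 − 55*f* (days) |
|---|---|---|---|
| 0.01 | 7.5 | 30 | 89.45 |
| 0.02 | 15 | 60 | 88.90 |
| 0.05 | 37.5 | 150 | 87.25 |

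**4. Effect on incidence.** Two quantities need to be kept apart.

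*(a) All-vaccinated against take-only incidence.* With *r* the event risk in non-takes relative to takes, the ratio is 1 − *f*(1 − *r*). At *r* = 0 the pooled figure is 1% to 5% lower (relative); at *r* = 0.5 it is 0.5% to 2.5% lower. If *r* is a true difference in risk, this gap would exist even if every subject were assessed at Day 90. It is a difference between two target quantities, not a consequence of the missing contact.

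*(b) Incidence on Days 36-90.* This isolates the missing contact. Suppose five events arise in the group scheduled for Day 90. The incidence is 5/*N* over all vaccinated and 5/[*N*(1 − *f*)] over those scheduled.

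| *N* | all vaccinated, per 1000 | scheduled, *f* = 0.01 | scheduled, *f* = 0.05 |
|---|---|---|---|
| 750 | 5/750 = 6.67 | 5/742.5 = 6.73 | 5/712.5 = 7.02 |
| 3000 | 5/3000 = 1.67 | 5/2970 = 1.68 | 5/2850 = 1.75 |

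The largest shift is 7.02 − 6.67 = 0.35 per 1000. The exact (Clopper-Pearson) 95% interval for 5/750 is 2.2 to 15.5 per 1000, and for 5/3000 it is 0.5 to 3.9 per 1000. A 10% relative shortfall in the Day 36-90 figure would need *f* = 0.10, which nothing in the documents supports.

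**The case for a change.** The strongest case for a change is that SAP section 1 is the only place where the SAP sets out the follow-up schedule, so a reader of the SAP alone is misled. The 2019 note attached to the SAP again refers to Day 90 without the exception. The non-take rate is unknown rather than known to be low: entry is possible 3 years after vaccination, re-entry is allowed, and the 2019 note reports undisclosed re-enrolments that may have come sooner. A corrected sentence, a few counts and one table for Days 0-35 and 36-90 would cost little, and SAP Appendix I lets the report authors add tables.

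Some of this stands. The text is inconsistent, and giving the number of non-takes and of planned and completed Day 90 contacts would help readers. Both are matters of wording and reporting detail that a report team can handle without altering the plan. Onset day and site inspection are already planned listings, so a period split could be programmed if non-takes proved numerous.

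The case for mandatory new tables is weaker. The study is single-arm and descriptive, and SAP section 7 plans no formal analysis. A take split may not be derivable, because SAP section 3.1 keeps anticipated mild reactions off the case report forms. Nor can visit records stand in for take status. A subject with no Day 90 record may be an exempt non-take, a missed contact or a withdrawal; for early withdrawals section 6.6 promises only that "efforts will be made to conduct the Day 90 safety follow-up with the subject". Defining the Day 36-90 denominator from those records could remove missed contacts from it and introduce an error the pooled table does not have.

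**Conclusion.** No change to the analysis follows. SAP section 1 and the protocol passages conflict on who has a Day 90 assessment and should be reconciled, but this is a clerical slip in an introductory sentence that no analysis rule uses. The shorter schedule for non-takes is a deliberate protocol choice with a stated reason. Related events are still followed to resolution or stabilization in everyone, and the pooled tables are valid summaries over all vaccinated subjects.

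On an assumed non-take rate of 1% to 5%, the effect specific to the missing contact is 1% to 5% in relative terms on Day 36-90 incidence. With five late events in 750 subjects that is at most 0.35 per 1000, far inside the sampling uncertainty. The judgement rests on non-takes being rare, as protocol section 7.8.1 indicates. A count of non-takes in the report, where site inspection data allow it, would show whether that holds. Tables by period or by take remain optional.

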2 STUDY OBJECTIVE

The objectives of study VA-008 are:

- To vaccinate plasma donors with the ACAM2000[®] smallpox vaccine thereby inducing an immune response resulting in high anti-vaccinia antibody titers. The collection of donor plasma will be used in the manufacturing of Vaccinia Immune Globulin Intravenous (VIGIV).

- To ensure the safety of plasma donors vaccinated with ACAM2000® through the implementation of risk factor screening procedures and the collection of post-vaccination safety data.

Donors are vaccinated under a clinical trial protocol to ensure adequate screening of risk factors and monitoring of potential reactions. This statistical analysis plan will only address the second objective of study VA-008: the assessment of safety data collected from plasma donors vaccinated with ACAM2000®.

3 STUDY ENDPOINTS

3.1 Safety Endpoints

Safety endpoints include adverse events and the assessment of peri/myocarditis symptoms at each study visit. Additional endpoints related to subject safety which were captured during the study include vaccination site inspection, laboratory results (hematology, blood chemistry, pregnancy tests and EKG (see protocol for details)), physical exams, concomitant medications and vital signs.

Anticipated vaccination reactions (as defined in the study protocol), which are typically mild and do not interfere with daily function, will not be characterized as adverse events and are not captured on the case report forms. However, any vaccination reaction which is of greater intensity or duration than expected (i.e., moderate or severe pain, requires medication or interferes with daily life) will be categorized as an adverse event. In addition, any vaccination scab that has not separated by 28 days after vaccination will be categorized as an adverse event.

4 ANALYSIS POPULATION

Safety analyses will be performed on the safety population, which includes all subjects who were vaccinated with ACAM2000® smallpox vaccine per protocol during the study.

5 MISSING VALUES

Missing data are assumed to occur at random and to be minimal, thus no imputation methods will be used.

All summary statistics will be calculated with missing values omitted from analysis. The sample size for summary statistics will be provided in all summary tables.

6 ANALYSIS METHODS

Adverse events will be coded by the MedDRA coding dictionary. The incidence, intensity and relationship of events to ACAM2000® will be evaluated through the use of frequency tables, by MedDRA system organ class and preferred term.

The adverse events causality will be reported by the principle investigator from the sites, and reviewed by the medical monitor on a monthly basis. The company assessed causality for the adverse events will be documented as part of the standard process of medical review. The

summary of adverse events by relatedness will be based on the final company causality assessment.

In order to calculate the incidence of adverse events, each subject will be counted only once within each system organ class and preferred term category. The total number of events will also be provided for each system organ class and preferred term. When intensity or relationship to ACAM2000® is considered, the subject will be counted once, within each system organ class and preferred term category, for each intensity or relatedness category.

The incidence of most common reported Adverse Events, defined as those reported by at least 5% of subjects, will be tabulated by system organ class and preferred term as described above.

All adverse events reported during the study will be listed individually by subject. The time to onset of each adverse event relative (in number of days) to the day of ACAM2000® administration (Day 0) will be provided.

Serious Adverse Events (SAEs) will be listed and summarized in the same fashion as for all adverse events, if applicable.

The assessment of peri/myocarditis symptoms will be listed individually over time, including Day 90 safety assessment.

To reduce the potential risk of adverse events associated with ACAM2000®, including pericarditis and/or myocarditis, the VA-008 protocol inclusion and exclusion criteria have been developed to exclude subjects with cardiac risk factors, consistent with ACAM2000® labeling. To mitigate the risk of enrolling at risk subjects and potentially jeopardizing subject safety it is suggested that an EKG be performed prior to vaccination with ACAM2000® smallpox vaccine in all potential subjects \geq 50 years old and for all subjects $<$ 50 with two cardiac risk factors including; severely or morbidly obese or higher obesity classification (BMI \geq 36); high blood pressure diagnosed by a doctor; high blood cholesterol diagnosed by a doctor and; diabetes or high blood sugar diagnosed by a doctor. Only these subjects that have successfully passed initial screening and inclusion/exclusion criteria will be required to have an EKG assessment during the screening visit. Clinical trial site personnel must be appropriately trained by a site investigator or sub-investigator who is a licensed physician, to recognize the symptoms of pericarditis and/or myocarditis. The clinical trial site will also be appropriately trained to administer the EKG. EKG results will be reviewed and interrupted by a Board-Certified Cardiologist offsite. The assessment of the EKG will be communicated from the offsite cardiologist to the PI at the clinical trial site and the sponsor team within 24 hours. The incidence of abnormal EKG results will be calculated for all the subjects with EKG results tested.

Concomitant medications will be coded and classified by the WHO drug dictionary. Concomitant medications will be listed individually, in full, using the WHO code.

Hematology, blood chemistry and vital signs will be listed and summarized for each visit. The incidence of abnormal laboratory results will also be summarized by visit. The EKG results will be listed and summarized as well.

Listings of pregnancy test results together with the screening assessment of the childbearing potential will be provided. A summary of pregnancy test results over time will be provided to identify any pregnant subjects during the study.

The abnormal results for physical exam will be included in the medical history results and listed.

All summary statistics for continuous variables will include the mean, standard deviation, median, minimum, maximum and sample size. Count and percentages will be provided for categorical variables.

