7.6 Assessment of Severity (intensity)

Assessments of AE/ADR severity are to follow the guidelines provided below:

Table 1 AE/ADR Severity Assessment

Intensity	Description
Mild	Awareness of a sign or symptom but subject can tolerate.
Moderate	Discomfort enough to cause interference with normal daily activity.
Severe	Resulting in an inability to do work or do usual daily activity.

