8.3 Planned Method of Analyses

The final study report will include tabulated data collected from subjects' eCRF. Adverse events will be coded using the MedDRA coding dictionary and will be listed and summarized. Summary of adverse events by relatedness will be based on the final Sponsor's causality assessment. Adverse events assessed as Definitely, Probably or Possibly Related will be considered as 'related' to the study drug (i.e., adverse reactions).

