14.1 Demographic Data

14.1.1 Summary of baseline demographic and other characteristics

14.2 Efficacy Data N/A

14.3 Safety Data

14.3.1 Displays of Adverse Events

14.3.1.1 Adverse events by system organ class and preferred term

14.3.1.2 Adverse events by system organ class, preferred term and relatedness

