14.3.1.3 Adverse events by system organ class, preferred term and intensity

14.3.1.4 Adverse events by system organ class and preferred term with incidence $\geq 5\%$ ¹

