14.3.1.9 Related adverse events by system organ class, preferred term and intensity

14.3.2 Listing of deaths and other serious adverse events

14.3.3 Narratives of death and other serious adverse events

14.3.4 Summary of laboratory values

14.3.4.1 Summary of blood chemistry results

14.3.4.2 Summary of hematology results

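### SAP 6 can count one donor in several intensity or relatedness columns, so the columns may overlap and need not add up to the overall adverse event incidence

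*SAP*

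**What the plan says.** SAP 6 has two counting rules. For overall incidence, "each subject will be counted only once within each system organ class and preferred term category". For intensity or relationship, "the subject will be counted once, within each system organ class and preferred term category, for each intensity or relatedness category". It adds event totals: "The total number of events will also be provided for each system organ class and preferred term".

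The second rule governs three tables in SAP Appendix I: "14.3.1.2 Adverse events by system organ class, preferred term and relatedness", "14.3.1.3 Adverse events by system organ class, preferred term and intensity" and "14.3.1.9 Related adverse events by system organ class, preferred term and intensity". SAP 6 summarises serious adverse events in the same way, so Tables 14.3.1.6 and 14.3.1.7 follow it too, if there are enough serious events to produce them.

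The categories come from the protocol. On intensity, section 7.6 says "Assessments of AE/ADR severity are to follow the guidelines provided below", and its Table 1 lists mild, moderate and severe. On relatedness, section 8.3 says "Adverse events assessed as Definitely, Probably or Possibly Related will be considered as 'related' to the study drug".

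SAP 6, the table list and Protocol 8.3 do not assign a donor to the highest intensity or the strongest relationship. Nor do they warn that the columns may overlap.

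**The concern.** A table of adverse events by intensity is normally read as a split of affected donors: so many had nothing worse than mild, so many reached moderate, so many reached severe. A table by relatedness is read the same way. Those readings require each donor to appear once per row. Under the SAP's rule a donor with a moderate and a severe event in one SOC appears under both, and a donor with a related and an unrelated event appears under both.

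Safety is the only objective that the SAP addresses (SAP 2), and no formal analysis is planned (SAP 7), so these frequency tables are the main summary of the study. If the columns overlap, the tables cannot show how many donors had at most mild events or only unrelated ones, and they will not reconcile to Table 14.3.1.1.

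**Working it through.** The documents state no figure that depends on this rule, so there is none to reproduce. The check applies both rules to a small constructed row and then gauges possible size.

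**1. Constructed row (one SOC or PT, three affected donors, five events)**

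- Donor 1: mild related, severe unrelated.
- Donor 2: mild related.
- Donor 3: mild related, moderate unrelated.

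Overall incidence, counting each donor once, is 3.

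| Table type | SAP 6 rule | One count per donor |
|---|---|---|
| Intensity: mild / moderate / severe | 3 / 1 / 1, sum 5 | 1 / 1 / 1, sum 3 |
| Relatedness: related / unrelated | 3 / 2, sum 5 | 3 / 0, sum 3 |

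The right-hand column uses maximum intensity and strongest relationship. Severe (1) and related (3) are the same under both rules, because any donor with a severe event, or with any related event, enters that column either way. Mild falls from 3 to 1 and unrelated from 2 to 0. Moderate does not change in this row, but would if Donor 1 also had a moderate event.

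**2. General form**

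If donor *i* has events in *k* distinct categories of a row, the columns exceed overall incidence by the sum of (*k* − 1) over affected donors. If a share *f* of affected donors have exactly two categories, column total ÷ overall incidence = 1 + *f*. Illustrative values: *f* = 20% gives 120%; *f* = 50% gives 150%. With three intensities the ratio cannot exceed 3. If *f* = 0, the columns add up exactly.

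**3. Scale**

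Inputs: 3% of previously vaccinated subjects with a severe event (SAP 7, citing the Investigator's Brochure) and 750 to 3000 donors (SAP 1). Assumptions: all severe donors fall in one row, and a share *q* of them also have events of one lower grade in that row. Excess = 0.03 × N × *q*.

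| *q* | N = 750 (22.5 severe) | N = 3000 (90 severe) | Percentage points |
|---|---|---|---|
| 0 | 0 | 0 | 0 |
| 0.25 | 5.6 | 22.5 | 0.75 |
| 0.5 | 11.3 | 45 | 1.5 |
| 1 | 22.5 | 90 | 3.0 |

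Putting all severe donors in one row makes this generous for overlap with the severe column. A donor present at all three grades would add two counts instead of one, and overlap between mild and moderate alone would come on top; the documents give no rate for either. The 3% is borrowed for scale only: SAP 7 defines severe there as interference with daily activities, which is closer to the moderate grade in Protocol Table 1.

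**4. Table 14.3.1.9**

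In the constructed row all three related events are mild, so the correct entry is mild 3, moderate 0, severe 0. Taking each donor's maximum over all events would give 1 / 1 / 1 and show a severe related case that never occurred. Worst-case counting must therefore restrict intensity to related events in this table.

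**The case against.** The case against is that this is a prespecified display choice and contradicts nothing in the documents. Several parts of it stand.

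- **Frequency.** A reader might infer that repeats are the normal case, since the vaccination site is reviewed at six scheduled visits from Day 3 to Day 35. The documents do not support that. Protocol 7.1 lists intensity as one attribute of an event, and nothing says that a new record is opened when the grade changes. Protocol 7.1 and 7.8.1 exclude expected mild vaccination reactions from adverse events, and SAP 3.1 says that they are not captured on the case report forms. Some overlap remains possible: malaise, fatigue, myalgia and headache are named as common events in Protocol 7.8 but are not among the expected responses in 7.8.1, and moderate/severe overlap is untouched. At SOC level two different terms at different grades are enough; at PT level the same term must recur.
- **Consequence.** A reader might infer that severe or related incidence is overstated, or that the 6% DSMB trigger in SAP 7 would shift. Neither follows, as the first step of the check shows: the trigger depends on whether a donor has a qualifying severe event, not on lower-grade columns.
- **Recoverability.** Event totals and individual listings would let a reader resolve overlap, but only by recounting donors by hand.
- **Unseen shells.** The 2019 note attached to the SAP refers to separate table shells, which are not among the documents reviewed. They might carry a footnote on overlap.

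**Conclusion.** The point holds as a conditional weakness in presentation. When a donor has events of different intensity or relatedness in the same row, the SAP's rule makes the columns overlap and lets them exceed Table 14.3.1.1. The mild, moderate and unrelated columns then cannot be read as at most mild, at most moderate or only unrelated. If a relatedness table shows the separate causality levels, the same applies to every level below the strongest.

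The size is unknown. It is zero if no donor has differently graded or differently attributed events in a row; the 3.0-point figure is a scale marker that rests on the assumptions stated with it. It would be wrong to say that the columns always overlap, or that the principal safety figures are misstated. Worst-case counting is still the better method for a plan whose only subject is safety. This is a cheap improvement, not a correction of an error.

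**What to change.** Replace the sentence in SAP 6 with:

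> In intensity tables each subject is counted once per SOC and per PT at the maximum intensity. In relatedness tables each subject is counted once per SOC and per PT at the strongest relationship. In Table 14.3.1.9 the maximum intensity is taken among related events only. The number of events in each category is shown alongside.

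Apply it to Tables 14.3.1.2, 14.3.1.3 and 14.3.1.9, and to 14.3.1.6 and 14.3.1.7 if they are generated. If the sponsor prefers the present rule, the minimum is a footnote on each table saying that the columns are not mutually exclusive and should not be summed.

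The cost is a short SAP amendment and a small reprogramming of tables that the 2019 note describes as already written. The trade-off is that a donor's lower-grade or unrelated occurrences in the same row would appear only in the event counts and listings.
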